Our study's design is a randomized controlled single blinded cross-over study. Overall designs will include two 12 weeks treatment periods separated by 8 weeks washout periods.

One group will have pacing-washout-placebo sequence while the other will have placebo-washout-pacing sequence. Subjects will be randomized to either pacing (intervention) or non-pacing (placebo) with 1:1 ratio at the initial visit. Each subject will undergo heart ultrasound (echocardiogram), symptoms/quality of life assessment, and 6 minute walking distance assessment at initial, 12, 20, 32 weeks visits. This type of clinical trial design will have an advantage of blinding the intervention to the subject which will minimize bias and would create a control group. Indeed, will allow still to use relatively small number of subjects with enough power to test outcomes comparable to single arm prospective trial design, while parallel randomized controlled studies design would require higher subjects numbers for reaching an adequate power to test outcomes of interest due to lack of self control.

This study will allow us to evaluate the effect of this intervention on heart failure symptoms, heart size and function as well as quality of life in this specific group of heart failure patients.

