## **VI. Main Hypothesis**

To determine whether cardiac resynchronization therapy by single right ventricular lead in heart failure patient with RBBB will be associated with positive reverse left ventricular remodeling and improvement in heart failure symptoms and quality of life.

Primary endpoint Positive reverse left ventricular remodeling, defined as increase in LV Ejection Fraction  $>15\%$  from baseline at 6 months.

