Cover Page for Statistical Analysis Plan

Sponsor-Investigator:	[name]
NCT Number:	NCT02441101
Unique Protocol ID:	201409760
Official Title:	Right Ventricular Septal Pacing in Patients With Right Bundle Branch Block and Heart Failure (The SPARK Trial)
Date of Document:	24 December 2014

Linear mixed model analysis for repeated measures will be used to test for change over the follow-up period in the primary outcome measures. Post-hoc pairwise comparison with baseline will be performed using Dunnett's test. Mean estimates at each time point, and mean change from baseline (with 95% confidence limits) will be computed from the fitted model. All tests were two-tailed and a $p < 0.05$ was considered as statistically significant. All analyses will be conducted using the intention-to-treat population.

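### The trial is a randomised two-sequence cross-over, but no contrast planned in the SAP compares pacing with non-pacing

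*SAP*

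**What the plan says.** **Design (Protocol, section I, Introduction).** Allocation is 1:1 and only the subject is blinded. "One group will have pacing-washout-placebo sequence while the other will have placebo-washout-pacing sequence". On timing: "Overall designs will include two 12 weeks treatment periods separated by 8 weeks washout periods". Echocardiography, symptom and quality-of-life assessment and the walk test share one schedule: "6 minute walking distance assessment at initial, 12, 20, 32 weeks visits". One reason given for the design is "blinding the intervention to the subject which will minimize bias and would create a control group". Another is that each patient serves as their own control.

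**Endpoint (Protocol, section VI, Main Hypothesis).** "Positive reverse left ventricular remodeling, defined as increase in LV Ejection Fraction" of more than 15% from baseline at 6 months. This too is a change from baseline and does not mention the non-pacing condition.

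**Analysis (SAP).** The statistical text is one paragraph. The test is stated as: "Linear mixed model analysis for repeated measures will be used to test for change over the follow-up period in the primary outcome measures". The contrasts: "Post-hoc pairwise comparison with baseline will be performed using" Dunnett's method. The estimates: "Mean estimates at each time point, and mean change from baseline (with 95% confidence limits) will be computed from the fitted model". Tests are two-sided at 0.05 in the intention-to-treat population. No treatment, period or sequence term is named, and the protocol has no statistical section that supplies one.

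**The concern.** The trial's question is whether pacing changes outcome relative to no pacing. The cross-over provides that comparison within each patient, and the protocol justifies the design on that ground. The stated analysis asks instead whether outcomes move over time and whether each visit differs from baseline.

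A change from baseline can occur without any pacing effect. Patients enter on an LVEF of 35% or less (Protocol, section VII), so some regression to the mean is plausible. An echocardiogram up to 6 months old may stand in for one at the initial visit (section VIII). An analysis that does not use the non-pacing condition cannot separate such movement from a pacing effect.

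The Background section says a positive result would prompt a large multi-centre trial. A change caused by drift, or a diluted estimate of a real effect, could misinform that decision.

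**Working it through.** **Inputs from the documents.** 40 patients, 1:1, so 20 per sequence; visits at weeks 0, 12, 20 and 32; two-sided 0.05. The documents give no effect size, SD, power or dropout, so the figure of 40 cannot be reproduced.

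**Step 1: what each contrast estimates (no numerical assumptions).** Let τ be the pacing effect and d12, d20, d32 the changes over time shared by both sequences. Assume full washout. Expected changes from week 0:

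| | Week 12 | Week 20 | Week 32 |
|---|---|---|---|
| Pacing first | d12 + τ | d20 | d32 |
| Placebo first | d12 | d20 | d32 + τ |
| Pooled | d12 + τ/2 | d20 | d32 + τ/2 |

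- Pooled by visit: half the effect plus drift at weeks 12 and 32, and drift alone at week 20.
- By sequence, or by condition (baseline, end of pacing, end of placebo): a paced visit gives τ plus drift. The comparator is still baseline.
- Cross-over contrast: ½{[(d12 + τ) − d32] − [d12 − (d32 + τ)]} = τ. The drift cancels.

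**Step 2: precision.** Assumed: continuous outcome in SD units, no dropout, equal SDs, common correlation ρ between visits of 0.5 to 0.8.

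- Cross-over contrast: SE = √((1 − ρ)/20) = 0.158 (ρ = 0.5) to 0.100 (ρ = 0.8).
- Pooled change at one visit: SE = √(2(1 − ρ)/40), which is the same value.
- For τ = 0.5 SD the signal-to-error ratio is 0.5/0.158 = 3.16 to 0.5/0.100 = 5.00 for the cross-over contrast. For one pooled visit it is 0.25/0.158 = 1.58 to 0.25/0.100 = 2.50.

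**Step 3: rejection rates.** Cross-over power comes from the noncentral t with 38 df. The rest are simulated for a model with subject and visit terms (117 residual df), with visits pooled and a Dunnett critical value of 2.379 for three comparisons. Drift is a constant shift at all visits after baseline.

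| | ρ = 0.5 | ρ = 0.8 |
|---|---|---|
| **τ = 0.5 SD, no drift** | | |
| Cross-over contrast | 87% | 99.8% |
| SAP time test | about 38% | about 77% |
| Dunnett, one given visit (week 12 or week 32) | about 19% | about 46% |
| Dunnett, at least one of weeks 12 and 32 | about 30% | about 62% |
| **τ = 0** | | |
| SAP time test, drift 0.1 SD | about 8% | about 15% |
| SAP time test, drift 0.25 SD | about 33% | about 72% |
| Cross-over contrast, either drift | about 5% | about 5% |

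**Step 4: the by-sequence reading.** Take the pacing-first week-12 change as a paired t test with n = 20, so SE = √(2(1 − ρ)/20) = 0.224 to 0.141. With τ = 0.5 SD and no drift, the ratio is 2.24 to 3.54 and power is about 56% to 92%. With τ = 0 and 0.25 SD drift, it is significant in about 19% to 39% of trials. Dilution is gone, but exposure to drift remains.

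**The case against.** **Pooling is an assumption.** The SAP lists no model terms at all, not even visit or subject, so a fit by sequence or by condition is compatible with it. This stands. A reader might infer that the SAP necessarily halves the effect, or that it would need about four times the patients. The documents do not support either as a general statement. The halving holds only if sequences are pooled, and the fourfold figure holds only for one pooled visit at a time. What does not depend on the reading is that every stated contrast is against baseline.

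**A mixed model could include treatment, and a pilot SAP may be brief.** It could, but the SAP does not say so. It is also not silent: it names a specific test and specific comparisons, and these do not answer the cross-over question. That makes it a wrong stated analysis, not merely missing detail.

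**The drift sizes are assumed.** This stands. At least 3 months of optimal medical therapy is required at entry, which limits drift from recent treatment changes. A reader might infer that a significant result under this SAP would probably be false. The documents give no drift size and do not support that; at 0.1 SD the excess over 5% is modest.

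**The illustration is not on the declared endpoint.** This also stands. The protocol defines a responder, while the calculations use a continuous outcome. The algebra in step 1 applies equally to responder proportions by visit.

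**Carry-over.** LVEF remodelling may not fully reverse in 8 weeks, and the SAP has no check for it. A reader might infer that carry-over can only dilute a week-12/week-32 contrast. That holds if the residual has the same sign as the effect. A rebound of opposite sign after pacing stops could inflate the contrast, and the documents rule out neither.

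**Conclusion.** The concern holds. The protocol sets up a randomised comparison of pacing with non-pacing, and no contrast in the SAP makes it. This follows from the text and the step 1 algebra and needs no assumed values.

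The size of the consequence is conditional. Under the step 2 assumptions with visits pooled, power for a 0.5 SD effect falls from 87% to 99.8% with the cross-over contrast to about 38% to 77% with the time test. With Dunnett it is about 30% to 62% at either of weeks 12 and 32. Without a pacing effect, the chance of a significant time test depends on a drift that the documents do not quantify.

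A reader might also infer that the design or its data cannot answer the question. They can: the scheduled visits support the right contrast, and only the analysis plan needs to change. It should be changed before the data are analysed. Carry-over is secondary, and the conclusion does not rest on it.

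**What to change.** In the SAP:

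1. **Primary analysis.** Fit a mixed model to weeks 12 and 32 with treatment, period and sequence terms, a random subject effect and week 0 as baseline. Report pacing minus non-pacing with a 95% CI.
2. **Endpoint visits.** Name weeks 12 and 32, the ends of the treatment periods, in place of 6 months, which matches no scheduled visit. If the responder definition (LVEF increase above 15%) stays primary, compare responders by treatment with a method that respects the pairing within patients.
3. **Description.** Keep means and changes by visit as descriptive output.
4. **Optional, secondary.** Report the between-sequence difference in week 20 minus week 0 with a 95% CI as a descriptive carry-over check. Add the randomised week-12 comparison, adjusted for week 0, as a sensitivity analysis.

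**Cost.** A few SAP sentences, one replaced primary model and up to two short extra analyses, with no new patients, visits or follow-up. The optional analyses are imprecise. The carry-over check has a 95% CI half-width of 2.024 × √(4(1 − ρ)/20), or 0.64 SD (ρ = 0.5) to 0.40 SD (ρ = 0.8), so it cannot exclude a modest carry-over. The week-12 comparison has a standard error √(2(1 + ρ)) = 1.73 to 1.90 times that of the cross-over contrast.

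### The protocol names one primary endpoint, but the SAP tests unnamed primary outcome measures (plural) at 0.05 each, with no ranking, success rule or adjustment across outcomes

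*SAP*

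**What the plan says.** - **Protocol, Section VI (Main Hypothesis).** One endpoint is labelled primary: "Primary endpoint Positive reverse left ventricular remodeling, defined as increase in LV Ejection Fraction" of more than 15% from baseline at 6 months. The hypothesis above it is wider. It asks whether the therapy "will be associated with positive reverse left ventricular remodeling and improvement in heart failure symptoms and quality of life".
- **Protocol, Section I (Introduction).** Besides the echocardiogram, the plan schedules "symptoms/quality of life assessment, and 6 minute walking distance assessment at initial, 12, 20, 32 weeks visits". Section VIII shows that the symptom and quality-of-life part is two instruments, the Minnesota questionnaire and SA-NYHA.
- **SAP (one paragraph).** The mixed model "will be used to test for change over the follow-up period in the primary outcome measures". These measures are not named, counted or ranked, and LVEF is not mentioned. The sentence that begins "All tests were two-tailed and a" sets p < 0.05 as the threshold for all tests. The only multiplicity method is for visits: "Post-hoc pairwise comparison with baseline will be performed using Dunnett's test".

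Neither document labels any outcome secondary, or says whether a positive trial needs one measure or all of them.

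**The concern.** The primary outcome should be fixed before the data are seen, and the two documents should name the same one. Here the protocol points to one LVEF endpoint and the SAP to an open set. The plural could be a slip. However, the three-part hypothesis and the four repeated clinical measures (LVEF, Minnesota questionnaire, SA-NYHA, 6-minute walk) make a plural reading plausible, and nothing in the SAP rules it out.

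What is at stake is the meaning of a positive result. With no named measure and no success rule, whichever outcome falls below 0.05 could afterwards be presented as primary. Depending on the rule then adopted, the overall false-positive rate might be 5% or well above it. Section II says that proof of remodelling and symptom improvement would create interest in a large multicentre trial, so it matters which result carries that claim.

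**Working it through.** **Inputs**

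- Per-test level: 0.05, two-sided (SAP).
- Number of primary measures, k: not given. Assumed 2, 3 or 4; four is the number of repeated clinical measures listed above.
- Correlation between test statistics, ρ: not given. Assumed 0, 0.5 and 0.8.
- Success rule: not given. Both candidate rules are worked through.

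**The plan's own figure.** The only relevant figure is 0.05, which is an input. With one primary outcome the formula returns it: 1 − 0.95¹ = 0.05.

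**Rule A: success on any one measure counts.** For independent tests the chance of at least one false positive is 1 − (1 − 0.05)^k:

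- k = 2: 1 − 0.95² = 0.0975
- k = 3: 1 − 0.95³ = 0.1426
- k = 4: 1 − 0.95⁴ = 0.1855

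For correlated tests, equicorrelated normal statistics were simulated (1,000,000 draws per setting). The result is the share of draws with at least one |z| above 1.96:

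| k (assumed) | ρ = 0 | ρ = 0.5 | ρ = 0.8 |
|---|---|---|---|
| 2 | 0.0975 | 0.0907 | 0.0777 |
| 3 | 0.1426 | 0.1257 | 0.0984 |
| 4 | 0.1855 | 0.1561 | 0.1138 |

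**Rule B: all measures must succeed.** The chance that all are significant cannot exceed the chance that a given one is. If any one measure has no true effect, the error is therefore at most 0.05. With no true effect on any measure and ρ = 0.8, the simulated values are 0.0218 for k = 2 and 0.0104 for k = 4.

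**What Dunnett's test covers.** There are three post-baseline visits (12, 20 and 32 weeks). Three unadjusted comparisons with baseline, at an assumed correlation of 0.5, would give about 0.125. Dunnett's test brings this back to 0.05, with a large-sample critical value of about 2.35 in place of 1.96. This works within one outcome. Rule A's inflation arises across outcomes and is untouched.

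**With the gap closed.** One primary outcome gives 0.05. If four measures were kept and each tested at 0.05/4 = 0.0125, independent tests would give 1 − (1 − 0.0125)⁴ = 0.0491.

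**Time point.** Six months is about 26 weeks (6/12 × 52). No visit falls there. In the cross-over it lies 26 − 20 = 6 weeks into the second treatment period, so the protocol endpoint cannot be copied into the SAP without reconciliation.

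**The case against.** A reader might infer that the trial has several unadjusted chances to claim success, and so an error rate well above 5%. The documents do not support that, for four reasons.

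- **The count rests on one noun.** The SAP lists no measures. It is loosely worded elsewhere, shifting from future to past tense for its significance rule, and the only place that names a primary endpoint is explicit and singular. The plural may be loose wording.
- **No rule lets any single success count.** A significance threshold is not a success criterion. The hypothesis joins its parts with an *and*; read as requiring all of them, it gives no inflation.
- **Not everything is unadjusted.** Comparisons of visits with baseline are covered by Dunnett's test.
- **The percentages are not the chance of a false claim of pacing benefit.** The SAP tests change over follow-up and change from baseline, and states no pacing versus non-pacing contrast. That is a separate problem, and these figures do not measure it.

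Two points of context also stand. This is a pilot with an estimated 40 subjects, where strict error control matters less than in a confirmatory trial. And Section VIII allows a recent echocardiogram (within 6 months) or walk test (within 3 months) to replace the one at the initial visit, so not every measure need be taken afresh at each visit.

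All of this limits the size of the point, but the mismatch remains. The hypothesis's *and* is not a stated decision rule, and the documents do not settle whether the plural is a slip.

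**Conclusion.** The point holds as a conflict between the documents that leaves the primary claim open to selection after the data are seen. Section VI has one primary endpoint; the SAP has an unnamed plural, each measure at two-sided 0.05, with no ranking, success rule or adjustment across outcomes.

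Its size is conditional. If any one success counted, the false-positive chance would be about 8–10% for two measures and 11–19% for four. If all had to succeed, it would be at most 5%. The number of measures and the correlation (0 to 0.8) are assumptions, and the documents choose neither rule. An inflated error rate is therefore a possible consequence of the SAP's silence, not an established property of the plan. For a pilot this is worth correcting before analysis, but does not by itself invalidate the trial.

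**What to change.** Replace the plural in the SAP with text to this effect:

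*The single primary outcome is LVEF as defined in Protocol Section VI, compared between the pacing and non-pacing periods. The Minnesota questionnaire, SA-NYHA and 6-minute walk are secondary, reported with 95% confidence intervals and without a confirmatory claim.*

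Three details are needed for the documents to agree:

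1. Reconcile the 6-month time point with the scheduled visits at 12, 20 and 32 weeks, and say which measurement is the baseline for each period.
2. State whether the increase of more than 15% is relative or in absolute LVEF points.
3. Keep the Section VI definition. It is a responder threshold, so the SAP must say how it is analysed alongside the linear mixed model for mean LVEF.

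If the sponsor wants claims on the other measures too, list the set in advance and apply Holm across it.

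The cost is mainly SAP wording, with a matching clarification of the time point in Section VI. No added subjects, visits or tests are needed. Stating the pacing versus non-pacing contrast does change the specified analysis, so it needs to be programmed. The downside is that symptom and quality-of-life results can no longer carry a stand-alone primary claim.
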